6.10.2. Prohibited Medications and Non-Drug Therapies

Medications prohibited at specific time intervals prior to Visit 1 (and at any time during the study) are identified in the Exclusion Criteria (Section 5.2).

NOTE: All COPD medications (except for rescue albuterol/salbutamol, mucolytics and oxygen) are prohibited during the randomised period of the study except during the treatment of a moderate/severe COPD exacerbation or pneumonia. In the event of an exacerbation or pneumonia, sites should attempt to follow protocol treatment guidelines (Section 12.7); however, treatment with any medication that the health care provider deems necessary is allowed. Caution is advised in using a LABA or LAMA to treat a subject currently taking study treatment as these additional medications may increase the risk of overdose. If necessary the investigator or other health care personnel may stop the

subjects study treatment temporarily in order to treat the COPD exacerbation. Subjects who require more than two consecutive 14 day courses of treatment (i.e. antibiotics or corticosteroids) should be evaluated for their continuation on study treatment by the investigator in consultation with the GSK medical monitor.

Eligible subjects will be allowed to continue their usual COPD medications during screening and the 2-week run-in period. On the morning of the Screening Visit subjects will refrain from taking their morning dose of their usual COPD medications until instructed to do so by clinic personnel. During the run-in period subjects will continue to use their usual COPD medications with no change in medication or dose.

The number of long-acting bronchodilators taken each day during the run-in period (0, 1 or 2) will be recorded.

On the day before the Randomisation Visit (V2), subjects will take their last dose of their usual COPD medications and will not use any other COPD medications (except for those allowed per protocol: rescue albuterol, oxygen, mucolytics and medications for the treatment of a COPD exacerbation or pneumonia) until the end of the study. Rescue albuterol/salbutamol can be used throughout the study as needed but must be withheld for at least 4 hours prior to conducting spirometry.

COPD Medications and non-drug therapies that are prohibited during the randomized portion of the study:

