- Demography may be captured at either the Pre-screen Visit or Screening Visit (for subjects who do not have a Pre-screen Visit).
- The IRT will be used for randomisation, emergency unblinding and study treatment supply management (Please refer RAMOS NG IRT manual for more information)
- At Screening Visit 1 both pre and post-bronchodilator spirometry will be conducted. Pre-bronchodilator spirometry will be performed prior to the subject taking their morning dose of their usual COPD treatment, between 6am and 11am and after withholding rescue albuterol/salbutamol for ≥4 hours.
- At Visits 2-5 (and the Early Withdrawal Visit), pre-bronchodilator spirometry will be performed prior to taking the morning dose of study treatment, between 6am and 11am and after withholding rescue albuterol/salbutamol for ≥4 hours.

- g. Patient reported assessments should be conducted in the following order and before other study assessments: SGRQ-C, BDI/TDI.
- h. Close out eDevice for any subject who fails to randomize, withdraws early, or completes Visit 5.
- i. Physical examination may include height, weight, blood pressure, temperature, heart rate.
- j. Vital signs must be performed prior to spirometry and prior to taking morning dose of study medication.
- k. ECG to be obtained 15 - 45 minutes post-dose at treatment Visit 5 and Early Withdrawal Visit (if possible). If a subject is not dosed at Early Withdrawal, then an ECG can be taken at any time during the visit
- l. Chest X-ray (PA and lateral) is required at Screening (or historical x-ray obtained within 3 months prior to Screening) and at anytime there is a suspected pneumonia or a mod/severe exacerbation.
- m. Pulse oximetry must be performed at V2 and anytime there is a suspected pneumonia or a moderate or severe exacerbation.
- n. PK subset A: PK samples of 120 subjects at selected sites, to be obtained at two time points at Visit 4: pre-dose and in the window 5 to 15 minutes post-dose.
PK subset B: PK samples of 60 subjects at selected sites, to be obtained and Visit 4: pre-dose, 5-15min, 45-90min, 2.5-4h, 6-8h, 10-12h, 23-24h post-dose.
- o. PK subset A: PK samples of 120 subjects at selected sites, to be obtained at two time points at Visit 5: 5 to 15 minutes post-dose and 45 to 90 minutes post-dose.
- p. The genetics blood sample should be taken at V5 or at any visit after Randomisation (V2).
- q. Haematology and chemistry panels will include liver chemistry, and potassium and glucose levels.

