9.2. Sample Size Considerations

9.2.1. Sample Size Assumptions

The sample size calculations use a one-sided 2.5% significance level and an estimate of residual standard deviation (SD) for trough FEV₁ at Week 24 of 220mL. The estimate of SD is based on mixed model repeated measures (MMRM) analyses of previous phase IIIA studies in COPD subjects. A study with 816 evaluable subjects for the primary analysis will have 90% power to determine non-inferiority of FF/UMEC/VI to FF/VI+UMEC based on trough FEV₁ at Week 24, when the margin of non-inferiority is 50mL and the true mean treatment difference is assumed to be 0mL.

It is estimated that approximately 20% of subjects who are randomised will either discontinue study treatment or be excluded from the Adherent population at Week 24, therefore approximately 1020 subjects will be randomised.

However, subjects who provide trough FEV₁ data prior to Week 24 and are in the Adherent population will be included in and contribute to the analysis and so the power of the study may be higher than stated here.

[figure not shown]

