Study Design	
 This is a phase IIIB, 24-week, randomised, double-blind, parallel group, multicenter study evaluating FF/UMEC/VI (100/62.5/25mcg) delivered via a single ELLIPTA ('closed' triple) plus matching placebo ELLIPTA versus FF/VI (100/25mcg) + UMEC (62.5mcg) delivered via two ELLIPTAs ('open' triple), all taken once daily. Subjects will be randomized 1:1 to either FF/UMEC/VI or FF/VI+UMEC. The randomisation will be stratified based on long-acting bronchodilator usage during the run-in (none, one or two long-acting bronchodilators per day). A study with 816 evaluable subjects for the primary analysis will have 90% power to determine non-inferiority of FF/UMEC/VI to FF/VI+UMEC based on trough FEV1 at Week 24, an estimate of residual standard deviation (SD) for trough FEV1 at Week 24 of 220mL, at the one-sided 2.5% significance level when the margin of non-inferiority is 50mL and the true mean treatment difference is assumed to be 0mL. Based on approximately 20% of subjects who are randomized discontinuing study treatment or being excluded from the mPP population at Week 24, approximately 1020 subjects will be randomised
Planned Analyses	
 No interim analyses are planned for this study.

Overview	Key Elements of the RAP
	
 All decisions regarding final analysis, as defined in this RAP document, will be made by Source Data Lock (SDL) prior to Study Data Tabulation Model (SDTM) Database Freeze (DBF) of the study data except for the identification of protocol deviation (PD) that require treatment details. The PD of taking incorrect treatment and treatment non-compliance (based on active treatment) will be identified following DBF.

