7.1.2. Planned Efficacy Statistical Analyses

Primary Statistical Analyses
Endpoint(s)

 ○ Trough FEV1
Model Specification

 ○ The primary endpoint of change from baseline in trough FEV1 will be analyzed in the mPP population, using a mixed model repeated measures (MMRM) analysis, including trough FEV1 recorded at each of Week 4, 12 and 24. The model will include covariates of baseline FEV1, stratum (number of long-acting bronchodilators per day during the run-in), Visit, geographical region, treatment and Visit by baseline interaction. A Visit by treatment interaction term will also be included to allow treatment effects to be estimated at each visit separately. ○ The variance-covariance matrix will be assumed unstructured. ○ Two models will be fitted; one with a response variable of trough FEV1, and one with a response variable of change from baseline in trough FEV1.
Handling of Missing Data for Analysis

 ○ No data were collected for subjects who prematurely discontinued study treatment. All missing and excluded data will be assumed to be Missing at Random (MAR). Sensitivity analyses to investigate the impact of this assumption will be conducted as described below.
Model Checking & Diagnostics

 ○ Refer to Appendix 11: Model Checking and Diagnostics for Statistical Analyses.
Model Results Presentation

 ○ Least Square (LS) mean and LS mean change from baseline with their corresponding standard errors (SEs) will be presented for each treatment by Visit, together with estimated treatment differences (FF/UMEC/VI vs. FF/VI+UMEC) and the corresponding 95% confidence intervals (CIs). ○ A plot of LS means change from baseline and 95% CIs from the model will be generated for each treatment by Visit.
Example SAS Code

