10.5.2. Baseline Definition & Derivations

10.5.2.1. Baseline Definitions

Parameter	Study Assessments Collected prior to dosing		Baseline Definition
	Screening	Week 0 (Pre-Dose)	
Efficacy			
Trough FEV1, Trough FVC	X	X	Week 0 pre-dose.
SGRQ total and domain scores		X	Week 0 pre-dose
Safety			
Vitals, Labs, ECGs	X		Most recent individual value prior to first dose (generally Screening but could be a test repeat).

NOTES :

- Unless otherwise specified, the baseline definitions specified in Section [10.5.2.1](#) Baseline Definitions will be used for derivations for endpoints / parameters and indicated on summaries and listings.
- Unless otherwise stated, if baseline data is missing no derivation will be performed and will be set to missing.

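### Adding the Screening pre-dose FEV1 to the primary model could narrow the non-inferiority interval and keep subjects who lack a valid Week 0 reading

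*SAP*

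**What the plan says.** SAP 7.1.2 gives the primary MMRM for trough FEV1: "The model will include covariates of baseline FEV1, stratum (number of long-acting bronchodilators per day during the run-in), Visit, geographical region, treatment", plus Visit-by-baseline and Visit-by-treatment terms. The SAS code in the same section carries one baseline variable. Protocol 9.4.2 describes the same single-baseline adjustment.

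The table in SAP 10.5.2.1 marks FEV1 as collected before dosing at both Screening and Week 0, but defines baseline as Week 0 only. Its general rule is: "Unless otherwise stated, if baseline data is missing no derivation will be performed and will be set to missing". The tipping-point analysis in SAP 7.1.2 does not impute subjects who have no baseline.

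The two readings are planned under matched conditions. Protocol 7.1, footnote e, says of Screening: "Pre-bronchodilator spirometry will be performed prior to the subject taking their morning dose of their usual COPD treatment, between 6am and 11am", with rescue withheld for at least four hours. Footnote f sets the same time window and rescue rule at Week 0, before the first dose of study treatment. Protocol 7.3.3.1 requires standardised vendor equipment. Protocol 6.10.2 fixes the background treatment: "During the run-in period subjects will continue to use their usual COPD medications with no change in medication or dose". Protocol 5.3 bars randomisation after a medication change, pneumonia or a moderate or severe exacerbation in the run-in.

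Outside the eligibility assessment, the Screening FEV1 is used only in descriptive summaries (SAP 6.1.4).

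**The concern.** The trial succeeds or fails on whether one confidence bound lies above -50 mL. A single FEV1 reading contains visit-to-visit noise. A second matched reading from before randomisation may remove part of it from the residual variance at no cost in data collection. Weeks 4 and 12 cannot do this job, because they are post-randomisation responses with their own treatment effect.

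The second issue is retention. A Week 0 value can be lost if the reading was unacceptable (SAP 7.1.1.1), or if it was taken after dosing or within four hours of rescue use (SAP 10.1.1). Protocol 5.3 does not make an acceptable Week 0 test a condition of randomisation. PROC MIXED drops records with a missing covariate. A subject could therefore be randomised, treated for 24 weeks and left out of the primary model and the tipping-point ANCOVA, although a usable Screening reading exists.

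**Working it through.** **1. The plan's own figure.** Inputs: "The sample size calculations use a one-sided 2.5% significance level" (Protocol 9.2.1); "A study with 816 evaluable subjects for the primary analysis will have 90% power to determine non-inferiority" (Protocol 9.2.1); "an estimate of residual standard deviation (SD) for trough FEV1 at Week 24 of 220mL" (SAP synopsis); "when the margin of non-inferiority is 50mL and the true mean treatment difference is assumed to be 0mL" (Protocol 9.2.1).

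- n per arm = 2 × 220² × (1.960 + 1.282)² / 50² = 407, or 814 in total, against 816 stated.
- Power at 408 per arm = Φ(50 / (220 × √(2/408)) − 1.96) = 90.1%.
- 95% half-width = 1.96 × 220 × √(2/408) = 30.2 mL. The 31 mL detectable effect in Protocol 9.2.1.1 agrees to within 1 mL.
- 816 / 0.8 = 1020 randomised.

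The plan's figures reproduce.

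**2. Gain from the second reading.** Let a, b and c be the correlations Screening–Week 0, Week 0–Week 24 and Screening–Week 24. The partial correlation of Screening with Week 24, given Week 0, is r = (c − ab) / √((1 − a²)(1 − b²)). The new residual SD is 220 × √(1 − r²). None of a, b and c is in the documents. Treating 220 mL as the SD after adjustment for one baseline is also an assumption: Protocol 9.2.1 attributes it to MMRM analyses of earlier studies without listing their covariates.

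Cases in which the two early readings are closer to each other than to Week 24:

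- a = 0.93, b = 0.85, c = 0.83: r = 0.0395 / √(0.1351 × 0.2775) = 0.204. SD 215.4 mL, half-width 29.6 mL, power 91.2%.
- a = 0.92, b = 0.85, c = 0.85: r = 0.329. SD 207.7 mL, half-width 28.5 mL, power 93.0%.
- a = 0.90, b = 0.85, c = 0.765: c = ab, so r = 0 and nothing is gained.

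Favourable case, all correlations equal to ρ: r = ρ / (1 + ρ). With an assumed total SD of 400 to 550 mL, ρ = √(1 − 220²/SD²) = 0.835 to 0.917. Then r = 0.455 to 0.478 and the variance cut r² is 21% to 23%. A 1000-run ANCOVA simulation at ρ = 0.85 gave half-widths of 30.3 and 26.9 mL with one and two readings.

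By size of the cut, at 408 per arm:

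| Variance cut | SD (mL) | Half-width (mL) | Power |
|---|---|---|---|
| 0% | 220.0 | 30.2 | 90.1% |
| 4% | 215.6 | 29.6 | 91.2% |
| 8% | 211.0 | 29.0 | 92.3% |
| 15% | 202.8 | 27.8 | 94.1% |
| 21% | 195.5 | 26.8 | 95.5% |
| 23% | 193.0 | 26.5 | 95.9% |

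**3. Missing Week 0.** The rate is not in the documents. An assumed 0.5% to 5% of 816 is 4.1 to 40.8 subjects. With 408 × (1 − rate) per arm and SD 220 mL, the half-width is 30.3 to 31.0 mL and power 89.9% to 88.6%.

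**4. Cost in the model.** One term for Screening FEV1 and two for its interaction with three visits: 3 df against about 800 subjects.

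**The case against.** The strongest reply is that nothing is wrong. Adjusting for one pre-dose baseline is coherent, unbiased under randomisation and what the protocol specifies. Enrolment has already bought some margin: the regional counts in SAP 10.8.1 sum to 398 + 252 + 215 + 194 = 1059. With the planned 20% loss that leaves about 847 evaluable and power of about 91.1%. Even an assumed 5% loss of Week 0 values would then leave about 89.7%. Every size quoted for the gain is an assumption, and the plausible range includes zero. Leaving subjects without a baseline unimputed is an explicit choice in the SAP.

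The remedy can also be done badly. A Screening covariate without a fill-in rule would drop subjects who lack an acceptable Screening value. Using Screening in place of Week 0 would mix two baseline definitions in the reported changes. Screening is also the eligibility visit, so its values are affected by selection.

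Most of this stands, and it limits the point to an optional efficiency gain. It does not show harm. Both readings precede randomisation and selection acts equally on both arms, so adjustment does not bias the treatment difference. The practical objections are answered by how the rule is written.

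A reader might infer three stronger things, none of which the documents support. The first is that the primary analysis is invalid or underpowered; it is neither on the stated assumptions. The second is that a cut of 21-23% should be expected; that needs equal correlations, which is unlikely with readings about 2 weeks apart on the same medication and an outcome 24 weeks later on new treatment. The third is that every subject has two usable readings; both are planned, but either can be missing or unacceptable.

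**Conclusion.** The point holds as a low-cost improvement in precision and retention. On assumed correlations, a residual-variance cut of 0-15% is the plausible range. At the top of that range the gain is worth 816/0.85 − 816 = 144 extra evaluable subjects; at the bottom it is worth nothing. The favourable upper case of 21-23% gives a half-width of about 26.7 mL and power of 95-96%. The retention benefit cannot be sized from the documents and is modest at the rates assumed here. The conclusion rests on Screening FEV1 carrying some information about Week 24 beyond Week 0. That is likely for a noisy measurement, but the documents do not establish it.

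**What to change.** Before unblinding, and listed in SAP 2.1 as a change from the protocol's model:

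- Add Screening pre-bronchodilator FEV1 and its Visit interaction to the trough FEV1 MMRM for the mPP and ITT populations, and Screening FEV1 to the tipping-point ANCOVA.
- Keep Week 0 as the reference for reported change from baseline.
- If one of the two pre-dose readings is missing or invalid, fill it with a treatment-blind prediction from the other, for example a regression on the other reading pooled over arms. No subject with at least one acceptable pre-dose reading is then dropped for lack of a baseline. Amend the missing-baseline rules in SAP 10.5.2.1 and in the tipping-point text to match.

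The cost is 3 model df, a fill-in rule likely to affect few subjects, and a small update to the LS-means code so that it also averages over the Screening covariate. No new data, visits or change of estimand are needed.

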5.1. Handling of Missing Data

The primary estimand for this study is a ‘de jure’ estimand. The primary analysis will use an ‘MPP’ population, using only data collected on-treatment and excluding data following protocol deviation or other event considered to impact the primary efficacy endpoint of change from baseline in trough FEV1 (as detailed in Section 10.1.2). This will evaluate the treatment difference if all subjects had taken the treatment as directed in the protocol which is considered the appropriate estimand for a determination of non-inferiority.

All data excluded from the primary efficacy analysis will be assumed to be missing at random. The sensitivity of the results to this assumption will be investigated by use of a ‘tipping point’ analysis as described in Section 7.1.2. This will evaluate various assumptions for the mean change from baseline in trough FEV1 for data excluded from the primary analysis, including scenarios where the response to treatment on FF/UMEC/VI is worse than that on FF/VI + UMEC and vice versa.

An alternative estimand will be evaluated. This will use the ITT population using all data collected on-treatment, for the change from baseline in trough FEV1. (No off-treatment

data for trough FEV1 were collected in this study.) All missing data will be assumed to be missing at random. This will evaluate the treatment difference in all randomized subjects, regardless of adherence to the protocol but assuming the treatment effect for subjects who discontinued treatment was similar to that for those who completed treatment.

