<pre>proc mixed data=<dataset>; class treatment visit cengroup stratum subjid; model endpoint=baseline stratum visit cengroup treatment visit*baseline visit*treatment / ddfm=kr; repeated visit/ subject=subjid type=un; lsmeans visit*treatment / cl diff e om=OMdset at (baseline)=(&blm.); ods output lsmeans=lsmeans; ods output diffs=diffs; run;</pre> 
where OMdset is a dataset with a row for every subject-visit combination that contains all of the covariates and blm is a macro variable containing the mean baseline for the subjects used in the analysis. This is used to derive the LS means using coefficients which are based on the subjects used in the analysis.

Sensitivity and Supportive Statistical Analyses

 ○ The above will be repeated for the ITT population. LS mean and LS mean change from

Sensitivity and Supportive Statistical Analyses

baseline with their corresponding SEs will be presented for each treatment by Visit, together with estimated treatment differences and the corresponding 95% CIs.

- A “tipping point” sensitivity analysis of trough FEV1 at Week 24 will be conducted for the mPP Population. This will explore the impact of missing data by using differing assumptions regarding the mean treatment effect in subjects who discontinue study treatment or have data excluded from the mPP Population analyses. Mean treatment effects investigated will range from a change from baseline of -150mL to +150mL in increments of 50mL. For each value of the assumed mean change from baseline on FF/UMEC/VI, the full range of values for the assumed mean change from baseline for FF/VI+UMEC will be investigated; thus including scenarios where subjects who discontinue FF/UMEC/VI have a lower treatment effect than those who discontinue FF/VI+UMEC and vice versa. The analysis results will be used to explore the conditions under which the conclusion of non-inferiority no longer holds.

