10.1.2. Exclusions from mPP Population

The full list of protocol deviations collected on the eCRF is in the PDMP.

The mPP Population is the primary analysis population, comprising all subjects from ITT population with the exception of:

- Full exclusion: subjects who have a full protocol deviation considered to impact primary endpoint (trough FEV1)
 - Eligibility criteria (those that impacts primary endpoint as listed in PDMP, [Appendix 2](#)) not met
 - Treatment non-compliance (overall compliance <80% or >120% over the 24-week treatment period, based on active treatment)
 - Randomisation criteria not met
 - Pneumonia or moderate/severe COPD exacerbation during run-in
 - Any change to COPD maintenance medications (including dosage and regimen) during the run-in
 - Antibiotics for respiratory tract infections during the run-in
- Partial exclusion: subjects who have a protocol deviation considered to impact primary endpoint. Trough FEV1 assessments collected after the incidence of the protocol deviation will be excluded from primary analysis.
 - Subject received incorrect container which contains incorrect study treatment.
 - Subjects took prohibited medication during treatment period, as detailed in PDMP [Appendix 3](#) Prohibited Medication.

- Partial exclusion: other events (not a protocol deviation) considered to impact the primary endpoint. Trough FEV1 assessments collected on or after the event start date will be excluded from primary analysis.
 - Subjects had a moderate/severe COPD exacerbation
 - Subjects had pneumonia.
 - Subjects who were unblinded by GCSP due to safety concerns.

Note: Subjects who received incorrect treatment and non-compliance based on active treatment will be identified as important PDs and flagged as PP exclusionary following treatment unblinding. These PDs will be flagged as PP exclusionary in ADaM DV dataset and will be included in summary of exclusion from mPP population table.

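### SAP 5.1 has the tipping-point analysis test all data excluded from the primary analysis, but SAP 7.1.2 runs it on mPP, which omits fully excluded subjects

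*SAP*

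**What the plan says.** SAP 5.1 treats all data left out of the primary analysis as missing at random, pointing to SAP 10.1.2 for the exclusions. Of the tipping-point analysis it says: "This will evaluate various assumptions for the mean change from baseline in trough FEV1 for data excluded from the primary analysis".

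SAP 10.1.2 lists two kinds of exclusion. The first is "Full exclusion: subjects who have a full protocol deviation considered to impact primary endpoint (trough FEV1"), which covers unmet eligibility criteria, unmet randomisation criteria, and overall compliance outside 80% to 120%. These subjects leave the population altogether. The second is partial: after an exacerbation, pneumonia, prohibited medication or incorrect treatment the subject stays in mPP and only later data are dropped.

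SAP 7.1.2 then states that the "sensitivity analysis of trough FEV1 at Week 24 will be conducted for the mPP Population". SAP 10.7.2.2 repeats this, Protocol 9.4.2 says the same under the older name Adherent Population, and Table 2.11 in SAP 10.13.5 is listed for MPP only. The grid gives each arm an assumed mean change from -150 to +150 mL in 50 mL steps, which makes 7 x 7 = 49 pairs.

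**The concern.** The tipping-point analysis exists to show how bad the unseen data must be before non-inferiority fails. If part of the excluded data never enters it, the imputed share shrinks and a larger arm gap is needed to overturn the result.

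The part at issue is not obviously neutral. Non-compliance arises after randomisation. Under SAP 10.6.2 it is judged on one inhaler in the FF/UMEC/VI arm and on the mean of two in the FF/VI+UMEC arm. Under SAP 3.1 and 10.1.2 it is flagged only after unblinding. None of this shows that exclusions will be unbalanced, but it is the kind of exclusion for which MAR should be stressed.

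**Working it through.** **Inputs.** From Protocol 9.2.1: "The sample size calculations use a one-sided 2.5% significance level"; "A study with 816 evaluable subjects for the primary analysis will have 90% power", "when the margin of non-inferiority is 50mL and the true mean treatment difference is assumed to be 0mL"; and a combined loss of about 20%, giving 1020 randomised. From the SAP synopsis: "an estimate of residual standard deviation (SD) for trough FEV1 at Week 24 of 220mL", and "Subjects will be randomized 1:1 to either FF/UMEC/VI or FF/VI+UMEC". The documents do not split the 20% between discontinuation, partial exclusion and full exclusion.

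**The plan's own figure.** n per arm = 2 x 220² x (1.960 + 1.282)² / 50² = 407, so 814 against the stated 816. With 408 per arm, 50 / (220 x √(2/408)) = 3.246, and 3.246 - 1.960 = 1.286, which gives power 0.901. Then 816 / 0.80 = 1020, so 204 subjects have no Week 24 value in the primary analysis. The sample size reproduces and is not in dispute.

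**Tipping gap.** Let N be the number analysed, f the imputed share, d0 the observed difference, and g the imputed FF/UMEC/VI minus FF/VI+UMEC gap:

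lower bound = (1 - f) x d0 + f x g - 1.96 x 220 x √(4/N)

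Setting this to -50 with d0 = 0 gives g = -(50 - 1.96 x 220 x √(4/N)) / f.

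**Assumptions.** Losses are equal by arm and the SD is 220 mL for observed and imputed values alike. Let e be the full exclusions as a percentage of the 1020. On the mPP-only reading, N = 1020 x (1 - e) and the number imputed is 204 - 1020 x e.

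| e | N | Imputed | f | CI half-width (mL) | Tipping gap (mL) | Failing pairs of 49 |
|---|---|---|---|---|---|---|
| all 204 imputed | 1020 | 204 | 20.0% | 27.0 | -115 | 10 |
| 2% | 1000 | 184 | 18.4% | 27.3 | -124 | 10 |
| 5% | 969 | 153 | 15.8% | 27.7 | -141 | 10 |
| 8% | 938 | 122 | 13.0% | 28.2 | -168 | 6 |
| 10% | 918 | 102 | 11.1% | 28.5 | -194 | 6 |
| 12% | 898 | 82 | 9.1% | 28.8 | -233 | 3 |
| 15% | 867 | 51 | 5.9% | 29.3 | -352 | 0 |

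For example, with all 204 imputed: (50 - 27.0) / 0.20 = 115.

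**Where the grid changes.** Arm gaps on the grid are multiples of 50 mL. The pairs at -150, -200, -250 and -300 number 4 + 3 + 2 + 1 = 10. The count drops to 6 once the tipping gap passes -150. At e = 6%, N = 958.8 and f = 142.8 / 958.8 = 14.9%, so the gap is -(50 - 27.85) / 0.149 = -149. At e = 6.5%, N = 953.7 and f = 137.7 / 953.7 = 14.4%, so the gap is -153. The planned table therefore changes only above about 6 points.

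**Other observed differences.** At d0 = -10 mL the tipping gap moves from -75 mL (all imputed) to -114 mL (e = 10%). At d0 = +10 mL it moves from -155 to -274 mL.

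**Random draws.** A simulation gave mean lower bounds within about 1 mL of the formula. With one random draw per subject, the bound itself varies with an SD of about 6 mL when all 204 are imputed and about 5 mL at e = 10%, so a cell near the boundary could fall either way.

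**The case against.** A reader might infer that fully excluded subjects are definitely never imputed. The documents do not establish that. Straight after naming mPP, SAP 7.1.2 directs the assumptions at subjects who discontinue or whose data are excluded from the mPP analyses. It then imputes every subject whose Week 24 value is missing or excluded, with missing baseline as the only stated exception. Read with 5.1, this could include full exclusions. Against that, SAP section 4 uses the same language of excluded data for partial deviations, whose subjects remain in mPP. Within an analysis specified for mPP, that is the more natural sense. The text still allows two different imputation datasets.

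A reader might also infer that the ITT analysis gives no protection because it too assumes MAR. That goes too far. A non-compliant or ineligible subject who attends Week 24 has an observed value, and the ITT mixed model uses it. MAR is then needed only for values that are truly missing. What remains is that this repeat varies no assumption about missing values. SAP 7.1.1 says primary-endpoint outputs are repeated on ITT, but SAP 10.13.5 lists no ITT tipping-point table, although the other trough FEV1 tables on mPP have an ITT counterpart.

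Two further points stand. Eligibility and randomisation-criteria failures predate treatment, so among full exclusions only non-compliance can be a consequence of it; exacerbation, pneumonia and prohibited medication are already partial exclusions inside mPP. Replacing a fully excluded subject's observed value with a draw is also a choice tied to the de jure estimand, though it is the one SAP 5.1 describes.

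**Conclusion.** The scope stated in SAP 5.1 and the population named in 7.1.2, 10.7.2.2 and Table 2.11 do not match. On the natural mPP-only reading, robustness is overstated in every scenario computed. The amount depends on a full-exclusion rate that the documents do not give: 9 mL at 2 points, 26 mL at 5 and 79 mL at 10, measured from -115 mL. The 5- and 10-point cases mean that a quarter and a half of the 204 losses are full exclusions (51 and 102 subjects). At about 6 points or fewer the planned table would show the same count of failing cells.

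These figures assume balanced losses, an SD of 220 mL and, for the main series, an observed difference of 0. SAP 7.1.2 takes the imputation SD from observed changes from baseline, which may differ from the residual 220 mL. The primary analysis, margin and sample size are unaffected. Clarifying the imputation set is a cheap improvement to a sensitivity analysis.

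**What to change.** In SAP 7.1.2, 10.7.2.2 and Table 2.11, define the imputation set as all ITT subjects with a baseline FEV1 whose Week 24 value is missing or excluded from the primary analysis, full exclusions included. Use observed values only where they are eligible for the primary analysis. Keep the mPP-only version alongside, report full exclusions by arm and reason, and record the departure from Protocol 9.4.2 in SAP 2.1, which at present lists only the change of population name. Fix the rule before unblinding, even though the non-compliance flags come later. If the sponsor prefers mPP only, SAP 5.1 should be narrowed to match.

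Replacing mPP by ITT in the text would not achieve this. Under the ITT data rules in SAP 10.1.1, excluded Week 24 values, including those after an exacerbation, would return as observed, so fewer subjects would be imputed.

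The cost is one extra table and a newly defined imputation flag. The grid and the ANCOVA model stay as they are, and no new data are needed.
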